6.10.6. Electrocardiograms

For ECG parameters that collected in triplicates, the arithmetic mean from the 3 measures for the same parameter at the same visit will be calculated and use for all subsequent analyses. This will include ECG heart rate (HR) in bpm, QRS complex (msec), and PR interval (msec), as well as the time elapsed between the onset of ventricular depolarization and the end of ventricular repolarization (QT) and QT corrected by HR values using Fridericia's formula (QTcF). QTcF in milliseconds (msec) will be reported. Descriptive statistics for the absolute values and changes from baseline for the ECG parameters (HR, PR interval, QRS, QT, QTcF) will be presented by treatment arm. Additional summary statistics for abnormal values (categorized as Low or High as shown in Table 6.5) will be provided. An MMRM-based model similar to the supportive analysis of the primary outcome will also be used for the change from baseline in HR, PR, and OTcF.

 Table 6.5.
 Electrocardiogram Abnormal Categories

Measure	Low	High
PR Interval	<120 msec	≥220 msec
QRS Interval	<60 msec	≥120 msec
HR	<50 and decrease of ≥15 bpm	>100 and increase ≥15 bpm
QT	NA	>500 msec
QTcF	NA	>450, >480, and >500 msec

Abbreviations: bpm = beats per minute; HR = heart rate; NA = not applicable; QTcF = QT corrected values using Fridericia's formula.

In addition, LY3298176 concentration-response analysis of QTcF and RR results may be performed, using figures that display change from baseline in QTcF on the vertical axis versus LY3298176 concentration (from PK/PD) on the horizontal axis, time-matched with the QTcF measurements. The figures will also include a regression line and corresponding regression analysis.

Summaries of categories for absolute observations and change from baseline for QTcF intervals will be provided as well, with absolute categories as >450, >480, and >500 msec and change from baseline categories as >30 msec and >60 msec.

6.10.7. Renal Safety

To assess renal safety, a summary and analyses use similar MMRM model as the supportive analysis for primary parameter will be performed for renal functional laboratory measures: estimated glomerular filtration rate (eGFR), creatinine, urine albumin/creatinine ratio (uACR). A log transformation for the analysis of uACR may be performed.

The minimum eGFR value and the maximum creatinine, urine ACR will be used for baseline and postbaseline calculation to generate the shift table. The shift table will use eGFR cutoff (<30,

30-<60, 60-<90, and \geq 90 mL/min/1.73m²), creatinine (\leq 1 ULN, >1 and \leq 2 ULN, >2 and \leq 4 ULN, and >4 ULN), and UACR (<30, \geq 30 and \leq 300, and >300 mg/g). The overall randomized treatment comparison will be tested using a likelihood-ratio Chi-square test. The shift table for minimum eGFR for both baseline and post-first dose at Week 26 will be summarized.

To examine AE indicating decrease in renal function, the SMQ for acute renal failure and a LSC for chronic renal failure events will be used to search the clinical trial data base for events of interest. A listing will be provided with all detected TEAE from these categories.

6.11. Exploratory Analyses

Baseline will be the mean value of the 2 measurements prior to treatment for SMBG. The change from baseline of 7-point SMBG profiles, and PROs will be summarized and analyzed.

Immunogenicity will besummarized and analyzed.

Genetic markers will be evaluated for their contribution to the variability of LY3298176 pharmacology and will also be included as covariates in PK/PD model-based analyses if applicable.

6.11.1. 7-Point SMBG

The 7-point SMBG profile consists of pre-meal and 2-hour postprandial BG measurements for morning, midday, and evening meals, as well as a bedtime BG measurement. Analyses will apply to the changes from baseline in the following variables for 7-point glucose profiles:

- 1. pre-morning meal-fasting BG (mg/dL)
- 2. morning meal 2-hour (hr) BG (mg/dL)
- 3. pre-midday meal BG (mg/dL)
- 4. midday meal 2-hour BG (mg/dL)
- 5. pre-evening meal BG (mg/dL)
- 6. evening meal 2-hour BG (mg/dL)
- 7. bedtime BG (mg/dL)
- 8. morning meal 2-hour excursion (mg/dL)
- 9. midday meal 2-hour excursion (mg/dL)
- 10. evening meal 2-hour excursion (mg/dL)
- 11. mean of all meals 2-hour excursion (mg/dL)
- 12. mean of all 7-point BG (mg/dL)
- 13. mean of all pre-meals BG (mg/dL)
- 14. mean of all 2-hour postprandial BG (mg/dL).

The morning, midday, and evening meal 2-hour excursions (that is, variable 8 through variable 10) will be calculated for each meal as the 2-hour postprandial BG minus the pre-meal BG.

The change from baseline of 7-point SMBG profiles will be calculated using a similar MMRM-based model described in section 6.1.1. The corresponding baseline will be used in the

model instead of the baseline HbA1c levels. The MMRM model will include a term for the HbA1c stratification group.

6.11.2. Health Outcome/Quality of Life Measures

Health-related quality of life will be assessed using 2 self-rated questionnaires that provide standardized measures of patients' perceived current health status: the Ability to Perform Physical Activities of Daily Living (APPADL) and the Impact of Weight on Self-Perception (IW-SP) questionnaires. Patients will complete the questionnaires at specified clinic visits prior to any other visit procedures or after the patient has sufficiently recovered from the preceding visit procedures (for example, in the case of fasting).

For each questionnaire change from baseline at Week 12 and Week 26 in the transformed overall scores will be analyzed using MMRM model as described in section 6.1.1 An analysis for LOCF endpoint will also be performed.

Additional exploratory analyses may also be done to explore relationships in weight loss (such as BMI lowered by >5%) with better HbA1c, APPADL, and IW-SP.

6.11.2.1. Ability to Perform Physical Activities of Daily Living

The APPADL questionnaire is useful in evaluating weight loss interventions in individuals with T2DM. The APPADL contains 7 items that assess how difficult it is for patients to engage in certain activities considered to be integral to normal daily life, such as walking, standing, and climbing stairs. Items are scored on a 5-point numeric rating scale where 5 = "not at all difficult" and 1 = "unable to do."

A raw total APPADL score is calculated by summing the scores of the 7 items and dividing by the number of items (7). The raw APPADL total score ranges from 1 to 5. A transformed overall score is obtained by linearly transforming the raw overall score to a 0-100 scale, using the following transformation formula:

[(actual raw score – lowest possible raw score) / (highest possible raw score –lowest possible raw score)] x 100

For example, using the transformation formula, a raw APPADL total score of "3.0" becomes a transformed total score of "50.0" on a scale of 0 to 100:

$$[(3.0-1.0)/(5-1)]*100 = 2/4*100 = 50.0$$

Higher raw APPADL raw total scores and higher transformed APPADL total scores indicate better self-reported ability to perform physical activities of daily living.

6.11.2.2. Impact of Weight on Self-Perception

The IW-SP questionnaire contains 3 items that assess how often the patient's body weight affects how happy they are with their appearance and how often they feel self-conscious when out in public. Items are scored on a 5-point numeric rating scale where 5 = "never" and 1 = "always."

A raw total IW-SP score is calculated by summing the scores of the 3 items and dividing by the number of items (3). The raw IW-SP total score ranges from 1 to 5. To transform the IW-SP total score to a scale ranging from 0 to 100, the same transformation formula as for the APPADL scores is used. For example, using the formula, a raw IW-SP total score of "2.0" becomes a transformed total score of "25.0" on a scale of 0 to 100:

$$[(2.0-1.0)/(5-1)]*100 = 1/4*100 = 25.0$$

Higher raw IW-SP total scores and higher transformed IW-SP total scores indicate better self-perception.

6.11.2.3. Missing Data Imputation for Ability to Perform Physical Activities of Daily Living and Impact of Weight on Self-Perception

For both the APPADL and the IW-SP questionnaires, the following rule will be applied in the case of missing item scores. If >50% of item scores are available, then missing item scores will be imputed using the mean of the available item scores. For the APPADL, this means there must be \geq 4 item scores completed and for the IW-SP there must be \geq 2 item scores completed. If the data for any respondent does not meet this missing data rule (>50% of item scores completed), then the questionnaire total score for that respondent will be considered missing. For analyses, missing scores will be imputed using LOCF.

6.11.3. Pharmacodynamic or Biomarker Analyses

Change from baseline to 12 and 26 weeks in fasting fibroblast growth factor-21 (FGF-21), adiponectin, β-hydroxy butyrate, glucagon, insulin levels, and other biomarkers will be analyzed and summarized using the mITT population on treatment without rescue dataset.

The change from baseline of fasting FGF-21, adiponectin, β -hydroxy butyrate, glucagon, insulin levels, and the bone biomarkers (CTX-1, PINP, Osteocalcin) will be analyzed using a similar MMRM-based model as described in section 6.1.1. A data transformation may be applied if the normality assumption is violated. If data warrant, a subgroup analysis with age >50 years women for the bone biomarkers will be performed.

Additional exploratory analyses may be performed if deemed necessary.

Additional LY3298176 concentration-response analyses of exploratory biomarkers may be performed and will be detailed in the PK modeling plan.

6.11.4. Evaluation of Immunogenicity

6.11.4.1. Definitions of Sample ADA Status

At a high level, an individual sample is potentially examined multiple times, in a hierarchical procedure, to produce a sample anti-drug antibodies (ADA) assay result and potentially multiple cross-reactive antibodies assay results and multiple neutralizing antibodies (NAb) assay results. The cut points used, the drug tolerance of each assay, and the possible values of titers are operating characteristics of the assay.

It can be the case that the presence of high concentrations of LY will affect immunoassays, and conversely high levels of antibodies may affect the measurement of LY concentration. Thus, an LY drug concentration, assessed from a sample drawn at the same time as the ADA sample, plays a key role in clinical interpretation of a sample when the laboratory result is Not Detected (Table 6.6).

Table 6.6. Sample Anti-Drug Antibodies (ADA) Assay Results

Sample Laboratory Result	Explanation
Detected	ADA are detected and confirmed.
Not Detected	The raw result as reported from the laboratory indicates not detected. The clinical
	interpretation of such results depends other factors (see below).
NO TEST, QNS, etc.	Sample exists but was unevaluable by the assay

Table 6.7. Sample Clinical Anti-Drug Antibodies (ADA) Interpretation Results

Sample Clinical Interpretation	Explanation
ADA Present	ADA assay result is Detected
ADA Not Present	ADA assay result is Not Detected and simultaneous drug concentration is at a
	level that has been demonstrated to not interfere in the ADA detection method
	(ie, drug concentration is below the assay's drug tolerance level).
	For patients receiving placebo, drug concentration is not assessed and is assumed to be below the assay's drug tolerance level.
	If drug concentration was planned but is not available for a treatment-period sample, a Not Detected sample will be declared ADA Inconclusive.
ADA Inconclusive	ADA assay result is Not Detected but drug concentration in the sample is at a level that can cause interference in the ADA detection method.
ADA Missing	ADA sample not drawn, QNS, not tested, etc., causing there to be no laboratory result reported or the result is reported as "no test."

Parallel terminology applies for each type of cross-reactive and NAb. Importantly, each of these are distinct assays and, in general, have different assay operating characteristics.

6.11.4.2. Definitions of Immunogenicity Assessment Periods

Immunogenicity Baseline Observations: Baseline period for immunogenicity assessment for each patient includes all observations on or prior to first administration of study drug. In instances where multiple baseline observations are collected, to determine patient ADA status the last non-missing immunogenicity assessment prior to first administration of study drug is used to determine treatment-emergent status (see below). In this context, 'missing' includes explicit 'ADA Missing' results, as defined in Table 6.7.

Immunogenicity Postbaseline Period Observations: Postbaseline period observations for each patient includes all observations after the first administration of study drug.

6.11.4.3. Definitions of Patient ADA Status

Patient evaluable for treatment-emergent ADA (TE ADA): A patient is evaluable for TE ADA if the patient has a non-missing baseline ADA result, and at least 1 non-missing postbaseline ADA result.

Treatment-emergent ADA positive (TE ADA+) patient: A patient who is evaluable for TE ADA is TE ADA+ if either of the following holds:

- a. The patient has baseline status of ADA Not Present and at least 1 postbaseline status of ADA Present with titer ≥2*MRD, where the MRD is the minimum required dilution of the ADA assay.
- b. The patient has baseline and postbaseline status of ADA Present, with the postbaseline titer being 2 dilutions (4-fold) greater than the baseline titer. That is, the patient has baseline status of ADA Present, with titer 1:B, and at least 1 postbaseline status of ADA Present, with titer 1:P, with P/B ≥4.

Treatment-emergent ADA Inconclusive patient: A patient who is evaluable for TE ADA is TE ADA Inconclusive if ≥20% of the patient's postbaseline samples, drawn pre-dose, are ADA Inconclusive and all remaining postbaseline samples are ADA Not Present.

Treatment-emergent ADA negative (TE ADA-) patient: A patient who is evaluable for TE ADA is TE ADA- when the patient is not TE ADA+ and the patient is not TE-ADA Inconclusive.

6.11.4.4. Analyses to be Performed

The number and proportion of patients who are TE ADA+ will be tabulated by treatment group, where proportions are relative to the number of patients who are TE ADA evaluable, as defined above. The tabulation will include the number and proportion of patients with ADA Present at baseline, and the number and proportion of TE ADA+ patients exhibiting each type of cross-reactive antibodies and NAb. This analysis will be performed for (a) the active treatment period, and also for (b) the entire postbaseline period including follow-up.

A listing will be provided of all immunogenicity assessments for those patients who at any time had ADA Present. This includes the LY concentration from a simultaneous PK sample, and the clinical interpretation result (ADA Present, ADA Not Present, ADA Inconclusive, Missing). In the case of ADA Present, a titer will be included, and TE ADA+ observations will be flagged. Also included, for each cross-reactive antibodies and NAb assay that was performed, will be the clinical interpretation result.

A summary will be provided of the number and percentage of LY-treated patients experiencing specific TEAE (see Table 6.8) by patient TE ADA status (TE ADA+, TE ADA-, TE ADA Inconclusive). The PT will be ordered by decreasing incidence in TE ADA+ status group.

A listing will be provided of all TEAE alongside ADA data, for any patient who had ADA Present at any time (including baseline) or had any specific TEAE (see Table 6.8). This listing includes a time course of ADA (clinical interpretation result plus flags for samples meeting TE ADA+ criteria and for samples with cross-reactive antibodies and NAb present) along with the TEAE.

Table 6.8. Adverse Events for Analysis with Immunogenicity Results

Events satisfying Anaphylaxis standardized MedDRA query (SMQ) (narrow or broad) Events satisfying Hypersensitivity SMQ (narrow or broad) Events satisfying Angioedema SMQ (narrow or broad)

Events mapping to High Level Term (HLT) of Injection site reaction Events mapping to HLT of Infusion site reaction

The primary efficacy measure of change in HbA1c from baseline to 26 weeks will be examined in relation to ADA. The initial examination will be boxplots of change in HbA1c at 26 weeks compared to maximum observed titer (1 category for each titer value) during the active treatment period, for patients who were TE ADA+ during that period. An additional category will be provided for patients who were not TE ADA+ during the active treatment period.

Additional immunogenicity analyses as determined later may be presented. The relationship between antibody titers, the PK parameters, and PD response to LY3298176 may also be assessed.

6.12. Pharmacokinetic and Pharmacodynamic Analyses

This section provides a high level description of the population pharmacokinetic/pharmacodynamic (PK/PD) analysis. Initially, a PK model will be developed as described in subsequent sections. PK/PD models for HR, BP, body weight, glucose and HbA1c will subsequently be developed incorporating the structural model and parameter estimates from the developed PK model. Detailed descriptions are provided in the Population PK/PD Analysis Plan.

Drug concentration data will be combined with dosing information, covariate data (eg, age, sex, weight, BMI, ethnic origin, concomitant medications, and baseline of PD variables), and the corresponding time-of-event data to produce the NONMEM dataset for population PK/PD analysis. The PD or clinical endpoints that will be analyzed may include weight, fasting glucose, HbA1c, DBP and SBP and heart-rate. If ADA titers are detected from immunogenicity testing, then the impact of immunogenicity titers on LY3298176 PK or any relevant PD parameters may also be examined.

Univariate and bivariate descriptive statistics, along with plots of independent and dependent variables, will be assessed to verify appropriate data distributions and to identify potential data errors, missing data, and outliers, as described in detail in the Population PK/PD Analysis Plan.

The population PK and PK/PD dataset will be analyzed using the nonlinear mixed effects modeling program NONMEM with PREDPP. The data will be fit to provide estimates of the population PK and/or PD parameters and error terms. NONMEM uses the extended-least-squares fitting routine, which continues iteratively until a minimal value of the objective function (MOF) is reached.

Inter-subject variability will be assessed separately on each of the PK or PD parameters using an exponential error structure (ie, log-normal distribution of individual parameter values). Once inter-subject variability terms are selected, covariance between the terms may be assessed by application of the omega block. Proportional, additive, and combined proportional and additive error structures may be evaluated for the residual error. The criteria used in selecting the most

appropriate base model will be based on overall goodness of fit, MOF, and robustness of parameter estimates.

Once a structural and statistical model has been established, the effect of potential patient factors will be assessed. Potentially significant patient factors (age, weight, gender, and renal function among others) based on graphical assessment will first be tested individually for their effect on each of the relevant PK (eg, Ka, CL, V) or PD (eg, baseline, Emax, EC50) parameters. For the continuous covariates, a variety of linear and nonlinear models will be tested.

A full model will be developed by testing, in combination, those covariates individually identified as significant in the covariate selection step. Once the full model has been established, the process will be reversed. The significance of potential covariates will be confirmed by removing each covariate individually from the full model. The criterion for retention of a covariate in the final model is an increase of ≥ 10.828 point drop in MOF (p<0.001) when the covariate is omitted from the full model. In the case of physiologically related and highly correlated factors (eg, weight and BMI), only 1 of the alternative factors may be selected for inclusion.

The validity of the final model will be tested by multiple approaches. This may include but is not limited to objective function mapping, leverage analysis, and posterior predictive check.

6.13. Subgroup Analyses

The primary efficacy endpoint of HbA1c change from baseline at Week 26 will be summarized for the subgroups as defined for each of the grouping variables as follows:

- age (<65 years, ≥ 65 years)
- race (White, Non-White)
- ethnicity (Hispanic/Latino, Not Hispanic/Latino)
- gender (Female, Male)
- duration (years) of T2DM, from "Date Diagnosed" to informed consent date (< study median, ≥ study median)
- baseline HbA1c (<8/5%, $\ge 8.5\%$)
- metformin use at baseline (Yes, No)
- baseline BMI ($<30 \text{ kg/m}^2$, $\ge 30 \text{ kg/m}^2$
- country (US/Puerto Rico, Poland, Slovakia, Mexico).

If the value of a grouping variable cannot be determined for a patient, the patient will be excluded from the corresponding subgroup analysis.

The subgroup by treatment interaction will be assessed for the HbA1c endpoint with the following parameters in the ANCOVA model: baseline HbA1c (continuous), metformin use (yes, no), baseline BMI category, subgroup factor, treatment group, and subgroup-by-treatment group interaction. For subgroup analyses by baseline HbA1c, the HbA1c category (<8.5%, ≥8.5%) will be used to replace the continuous HbA1c measurement in the model. For all other subgroup variables, the categories as given above will be used to assess the subgroup-by-treatment interaction

The adjusted mean changes from baseline, SEs, 95% CIs within each treatment group as well as the difference in mean change from baseline and corresponding 95% CIs between each investigative treatment group and the placebo for each subgroup will be calculated. In addition, the corresponding subgroup-by-treatment interaction p-value from the model will be calculated. The nominal p-values for the subgroup-by-treatment interactions will not be adjusted for multiplicity.

Change from baseline in body weight will also be analyzed for the subgroup of BMI baseline category, and HbA1C baseline category.

6.14. Interim Analyses

6.14.1. Overview

There will be up to 3 interim analyses for this study. This study will not be stopped for either positive efficacy or futility at any interim analysis.

The first interim analysis will occur after 30% patients finishing 12 weeks of treatment. It will only include key safety data (demographics, discontinuations, exposure, TEAE, AESIs, SAE, vital sign, and some lab parameters) review. The second interim analysis will occur after approximately 90% patients finish 12 weeks of treatment. It will include some key efficacy and safety parameters to monitor the compound safety and to support preliminary Phase 3 dose selection. These 2 interims will be for internal business decisions. The third interim analysis will occur when all patients have completed the treatment part of the study (prior to completion of the follow-up phase for all patients) and will include all safety, efficacy, and PK data available through the 26-week treatment for all patients to determine Phase 3 doses. We will refer this as the primary DBL.

An Assessment Committee (AC) will be formed to review the first and second interim analyses. Any change on the study design based on an interim analysis will be determined by the AC. A number of pre-identified individuals may gain access to the limited unblinded data, as specified in the unblinding plan, prior to the interim or primary outcome DBL in order to initiate population PK/PD model development processes for interim and final analyses, as well as plan and prepare for Phase 3 studies. Statistical Analysis Center (SAC) will be authorized to evaluate unblinded interim analyses and prepare the reports for the AC to review. Information that may unblind the study during the analyses will not be reported to study sites or blinded study team until the study has been unblinded.

All study team members will be unblinded after the primary DBL.

The study team will perform periodic, blinded safety reviews during the study and if safety signals or concerns arise from these reviews, the AC may be called upon to review unblinded safety data in an unplanned interim analysis.

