6.15. Clinical Trial Registry Analyses

Additional analyses will be performed for the purpose of fulfilling the Clinical Trial Registry (CTR) requirements. For CTR analyses, an AE will be considered 'Serious' whether or not it is a TEAE. An AE will be considered to be in the 'Other' category if it is both a TEAE and not serious.

Analyses provided for the CTR requirements include the following:

- Summary of AEs, provided as a dataset which will be converted to an XML file. Both Serious AEs and 'Other' AEs will be summarized by treatment group and by MedDRA Preferred Term (PT).
- For each Serious AE and 'Other' AE, for each PT and treatment group, the following will be provided:
 - o the number of participants at risk of an event
 - o the number of participants who experienced each event PT
 - o the number of events experienced.

Consistent with ClinicalTrials.gov (National Institutes of Health [NIH] [WWW]) requirements, a threshold (at a maximum of 5%) for frequency of 'Other' AEs can be implemented rather than presenting all 'Other' AEs. The determination of a threshold will be based on the overall number of 'Other' AEs.

7. Unblinding Plan

The purpose of the unblinding plan is to detail the procedures that are in place to minimize bias while preparing for or conducting any summary or analysis of the data for AC reports, data reviews, dose selection (interim efficacy/safety only), and developing/refining exposure analyses. Additionally, this plan identifies personnel who will be unblinded during the study, including unblinding for the AC interim analyses in support of the AC meetings.

The access to subject treatment assignments will not be provided to the investigator and site personnel until DBL is authorized for the planned final analysis at the completion of the blinded study.

The access to subject treatment assignments will not be provided to the following personnel until the primary data lock is authorized for the third interim analysis at the completion of the treatment period:

- Lilly personnel with direct site contact
- Lilly personnel responsible for data entry and data validation
- Lilly study team not in the AC and/or SAC.

After DBL, the study team will be unblinded to the study data to prepare for the analyses for CSR. Investigators can be provided treatment assignments for their subjects when unblinding has occurred and the information will not impact scientific integrity or introduce bias after final DBL.

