7.1. Operational Procedures

The randomization code (treatment assignment) will be stored in the Lilly IWRS and will not be accessible to the blinded Lilly study team, except for those pre-specified in the unblinding plan to be unblinded, until the final DBL. Members from the SAC, AC, and the study global patient safety (GPS) scientist may be unblinded to data prior to the DBL. The SAC, composed of Lilly or Lilly designated third party organization (TPO) unblinded statistics personnel, PK/PD scientists and the PK/PD analysts (for efficacy/safety interim analysis only) will form a separate team from the Lilly blinded team. The SAC will obtain the randomization code from the unblinded data movement group in order to generate unblinded tables, figures, and listings (TFLs) for the AC. Membership is listed in Table 7.1 for each of the groups mentioned above.

Group Name	Group Members
Blinded Lilly study team	Lilly clinical study team personnel who work on the study and have
	direct site contact including the clinical research physician, CTM, data
	sciences and solutions, GPS personnel, and study monitors, etc, and non-
	site direct contact regulatory scientist, statistician(s). However, per Lilly
	procedure, for patient safety, the study GPS scientist will be unblinded to
	SAE patient-level data for patient safety.
Blinded Lilly statistics group	Lilly statisticians and statistical analyst(s)
SAC (unblinded)	Lilly statisticians and statistical analyst(s) or TPO statistical analysts
Unblinded PK/PD team scientists (part	Lilly study team PK/PD scientists and analyst(s), etc.
of the SAC)	
Assessment Committee	Lilly physicians, statisticians, and GPS personnel
Unblinded data movement group	Unblinded data movement representative
The program senior management	Lilly GIP/GLP senior medical director or above

Table 7.1. Study I8F-MC-GPGB Group Name and Membership

Abbreviations: CTM = clinical trial manager; GIP/GLP = glucose-dependent insulinotropic peptide/glucagon-like peptide; GPS = global patient safety; PK/PD = pharmacokinetics/ pharmacodynamics; SAC = Statistical Analysis Center; SAE = serious adverse event; TPO = third party organization.

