7.4.2. Primary Lock (Third Interim)

The third interim analyses will be performed at week 26, the end of treatment period including both safety and efficacy reviews. The data will be cleaned and locked. Results will be unblinded for the study team. Lilly PK/PD scientists may obtain unblinding information before the DBL in order to perform PK/PD model-based analysis if deemed necessary.

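### The SAP unblinds the whole study team, including site-facing and data-validation staff, at the primary lock in three places but only at the final lock in section 7.1; the exposure is limited to Visit 801 data.

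*SAP*

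**What the plan says.** **Release at the primary lock.** The third interim analysis is the primary database lock (DBL). SAP 6.14.1 places it after all patients finish treatment but "prior to completion of the follow-up phase for all patients", and adds that "All study team members will be unblinded after the primary DBL". The opening of SAP section 7 withholds assignments from three sponsor groups "until the primary data lock is authorized for the third interim analysis at the completion of the treatment period". The first group is "Lilly personnel with direct site contact", the second is data entry and validation staff, and the third is the study team outside the Assessment Committee and the Statistical Analysis Center. SAP 7.4.2, on the primary lock, says: "Results will be unblinded for the study team".

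**Release at the final lock.** SAP 7.1 says that the randomization code will "not be accessible to the blinded Lilly study team, except for those pre-specified in the unblinding plan to be unblinded, until the final DBL". Table 7.1 describes that team as including staff with "direct site contact including the clinical research physician", the trial manager and the study monitors. It also lists a regulatory scientist and statisticians who have no direct site contact.

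**Other statements.** Investigators and site personnel stay blind until the lock for the final analysis (SAP section 7). Protocol 7.3 limits knowledge of assignments before study completion to a minimum number of sponsor personnel. A later sentence in the opening of section 7, and SAP 7.3 and 7.4, refer to the DBL without saying which one.

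**The concern.** One group of people has two release points. If the primary-lock rule is followed, the monitors, trial manager, research physician and data-validation staff know each patient's arm while some patients still have Visit 801 ahead of them. Those staff raise queries on follow-up adverse events and can enter some follow-up data. The events then enter summaries that compare arms. If the final-lock rule is followed as written, the statisticians listed in Table 7.1 could not see the code when they are due to analyse the Week-26 data. Neither rule works well as it stands, and staff cannot follow both.

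**Working it through.** The plan states no figure here, so the check compares the passages and then sizes the window.

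| Place | Who | Released at |
|---|---|---|
| SAP 6.14.1 | every study team member | primary lock |
| SAP 7, opening list | site-facing staff; data entry and validation staff; rest of the study team | primary lock |
| SAP 7.4.2 | study team | primary lock |
| SAP 7.1 with Table 7.1 | blinded study team, site-facing and not | final lock, with an exception |
| SAP 7, opening | investigators and site staff | final lock |
| SAP 7 (later sentence), 7.3, 7.4 | study team or its reports | lock not named |
| SAP 7.5 | data transfers to the sponsor | described as unblinded after the final lock |
| Protocol 7.3 | sponsor personnel | minimum number before study completion |

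**1. Is it the same group?** Yes. Table 7.1 places site-facing staff in the blinded study team, and the section 7 list releases site-facing staff at the primary lock.

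**2. Does the exception in 7.1 remove the conflict?** It covers people pre-specified in the unblinding plan, and section 7 is that plan. If the exception takes in everyone on the section 7 list, it exempts the whole blinded team and the final-lock rule binds nobody. The sentence that follows it in 7.1 points to a narrower set: the Statistical Analysis Center, the Assessment Committee and the study's global patient safety scientist.

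**3. Does the protocol settle it?** Protocol 5.3 ends the trial at the last patient's last visit or procedure in the Schedule of Activities, which runs to Visit 801. Releasing the whole team before then sits badly with the minimum-number statement in Protocol 7.3. Protocol 5.1, however, describes sponsor blinding for the treatment phase.

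**4. Which data are exposed?** The Schedule of Activities lists diary review for adverse events, ECG, chemistry, lipase and amylase, and antibody testing at Visit 801. SAP 6.10.3 summarises treatment-emergent events over treatment plus follow-up. SAP 6.11.4.4 tabulates antibodies over the whole postbaseline period. Protocol 9.2.1.2.5 requires a work-up for raised pancreatic enzymes at Visit 801 and allows sponsor staff as well as site staff to enter data for pancreatic adjudication.

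**5. How long is the window?** Week 30 − Week 26 = 4 weeks for each patient. Let L be the weeks from the last patient's Week-26 visit to the primary lock. Patients still awaiting Visit 801 at the lock are those whose Week-26 visit fell in the last 4 − L weeks before that last Week-26 visit. The documents do not give L, so as an assumption:
- L = 0: Week-26 visits in the last 4 weeks
- L = 2: Week-26 visits in the last 2 weeks
- L = 4 or more: none on this count

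No visit rate is given either, so this cannot be turned into a number of patients.

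**The case against.** The strongest reply is that three places agree on the primary lock and only 7.1 clearly differs. SAP 7.5 concerns data transfers and does not say that the team is blind before the final lock. On this view the release is deliberate, the word final in 7.1 is a slip, and changing one word cures it. That stands in part: the primary-lock release may well be intended, and a one-word change would remove the inconsistency. It would not answer Protocol 7.3, and site-facing staff would still learn assignments during follow-up.

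It is also fair that 7.1 does not itself separate site-facing staff from others. Table 7.1 includes statisticians without site contact, so the split proposed here is a recommendation and cannot be attributed to 7.1. The SAP does use that dividing line elsewhere: 7.4.1.3 allows wider access to interim results only for people without direct site contact.

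The safeguards are substantial. Sites stay blind, laboratory tests are central unless otherwise noted (Protocol Appendix 2), and deaths, cardiovascular and pancreatic events are adjudicated independently. Treatment-emergent events are also summarised for the treatment period alone. SAP 7.2 has the site monitor check that assignments stay restricted from sites, although under 6.14.1 that monitor would know them.

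A reader might infer that the antibody follow-up of about 1 year is at risk too. The documents do not support that. Protocol 9.8.1 restricts it to patients with treatment-emergent antibodies after LY3298176, so selection already reveals the active drug and there is no comparison between arms to bias. SAP 7.5 also lets immunogenicity data arrive after the final lock.

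**Conclusion.** The conflict is real and should be resolved, but it is a minor point. It bears on judgment-dependent safety data at Visit 801 and, to a lesser degree, on antibody results, which come from an assay. It affects only patients not yet through Visit 801 at the primary lock, over about 4 weeks each, and their number is unknown. The conclusion rests on two readings: that the exception in 7.1 is not meant to cover the whole team, and that the primary lock does fall before follow-up is complete, as 6.14.1 says.

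A reader might go further and infer that the primary result is compromised or that site staff would learn assignments. Neither follows. The Week-26 data are cleaned and locked before the team is unblinded (SAP 7.4.2), and sites are kept blind until the final lock. No power, error rate or primary conclusion changes, and nothing in the documents shows that bias would in fact arise.

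**What to change.** Use one rule in SAP 6.14.1, the opening of section 7, 7.1 and 7.4.2:

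- At the primary lock, unblind only personnel without site contact who prepare the analyses and report. This includes the non-site statisticians whom 7.1 now keeps blind.
- Keep personnel with direct site contact, and those doing data entry and validation, blind until the final lock.
- Replace the bare DBL in section 7, 7.3 and 7.4 with primary or final.

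All four places need editing; changing 6.14.1 and section 7 alone would leave 7.1 and 7.4.2 in conflict with the new rule. The cost is SAP wording and continued access limits. The small downside is that site-facing and data-validation staff cannot help with unblinded reporting until the final lock.
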